#### Study Design

This will be a single-center, double-blinded randomized controlled study. The study is comparing blood loss and postoperative pain and swelling in two cohorts: patients undergoing BTB ACL reconstruction who receive TXA during surgery and patients who do not receive TXA. The intravenous tranexamic acid will be administered before surgery begins and after the tourniquet is released at the conclusion of the surgery. Blood loss will be measured via measuring the amount of blood in the drain at the conclusion of the surgery. Patients will be asked on postoperative day 1, 2 and 7 to rate their pain according to the VAS scale. Patients will have their knee swelling measured immediately postoperatively and at their one-week follow up visit. The swelling ratio is defined as the postoperative mean circumference of upper pole of patella and lower pole of patella divided by the preoperative values.[9]

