Information to be recorded pre-operatively includes age, sex, height, weight, BMI, and American Society of Anesthesiology (ASA) classification. Intra-operative information will also be recorded, including operative time, and estimated blood loss. During the surgery, a suction device is utilized to remove excess blood from the surgical site and sucked into the suction drain and placed into a measuring cup. We will measure the perioperative blood loss by looking at the measuring cup and seeing how much blood is inside. The objective is to have the average blood loss of the cohort receiving TXA less than the cohort not receiving TXA. Knee swelling postoperatively will be measured using the swelling ratio. The swelling ratio is defined as the circumference of the operative limb divided by the circumference of the contralateral limb. Pain severity scores at rest will be assessed by use of a visual analog scale (VAS; 0 = no pain, 10 =worst pain imaginable) at 0.5, 1, 1.5, 2, 4, 6, 24, and 48 hours as well as 7 days after surgery. Percocet consumption will be recorded at 24 hours, 1 day, 2 days and 7 days after surgery. Incidence of TXA-related side effects (nausea/vomiting, itching, anxiety, increased thirst, rapid heartbeat) in the first 24 hours will be noted. Time to discharge from the post-anesthesia care unit (PACU) and time to discharge from the hospital will be recorded. Patients will be in the study a duration of two weeks, until their post-operative follow up visit.

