#### **Data Analysis and Statistical Plan**

Statistical analysis will be performed using chi-squared and/or fisher's exact testing depending on size for binary variables. An a priori power analysis was conducted to estimate the minimum sample size needed to achieve 83% power (1 - b) at the .05 significance level which was calculated to be 50 patients. Therefore, we added 10 patients to account for potential exclusions, totaling 110 patients. Variables used in the power calculation were taken from the literature including an assumed effect size of 0.5 and standard deviation (SD) of 2. This large sample size will provide enough information to truly determine a difference between cohorts. This sample size and statistical analysis was used in similar studies looking at the effects of TXA in ACL

Version 2/26/20

reconstruction[5, 12].

Continuous variables will be compared with paired t-tests if the data is approximately normally distributed. If the data is not normally distributed, Mann-Whitney tests will be used. All protected health information will be removed prior to statistical analysis. We will use patient subjective pain, perioperative blood loss and knee swelling data as statistical endpoints. Subjective pain will be measured with the VAS (visual analogue scale), perioperative blood loss will be measured looking at blood loss from the suction drain after surgery. We are looking for a statistically significant difference in perioperative blood loss between the two cohorts. The swelling ratio is defined as the postoperative mean circumference of upper pole of patella and lower pole of patella divided by the preoperative values according to our previous study[9]. The endpoints must be statistically significant between the two cohorts to show TXA is effective.

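### Low priority: analysing swelling by ANCOVA on preoperative knee circumference, rather than by an unadjusted test of the post/pre ratio, costs almost nothing and may gain precision

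*Combined protocol and SAP*

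**What the plan says.** Swelling belongs to the secondary objective and is one of three statistical endpoints named in the Data Analysis and Statistical Plan. That section defines it as the mean of the postoperative circumferences at the upper and "lower pole of patella divided by the preoperative values". Study Design gives the same definition. Methods and Procedures uses a different reference: "circumference of the operative limb divided by the circumference of the contralateral limb".

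On timing, Study Design states: "Patients will have their knee swelling measured immediately postoperatively and at their one-week follow up visit".

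On the test, the plan reads: "Continuous variables will be compared with paired t-tests if the data is approximately normally distributed". The alternative is: "If the data is not normally distributed, Mann-Whitney tests will be used". No regression model or baseline covariate is specified for any endpoint.

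The list of preoperative data in Methods and Procedures begins "Information to be recorded pre-operatively includes age, sex, height, weight, BMI" and ends with ASA class. Knee circumference is not on it, although the post/pre ratio cannot be formed without it.

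**The concern.** Under the post/pre definition, the preoperative circumference enters the analysis only as a divisor. On the log scale this subtracts the baseline with a weight of exactly 1, whatever the data show. ANCOVA estimates the weight from the same measurements.

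There is reason to doubt that the weight is 1. The Rationale describes the acute injury phase as including an effusion, and the listed eligibility criteria set no limit on time from injury to surgery. A preoperative reading may therefore contain variable, temporary swelling and tape error as well as knee size, and both pull the slope below 1. Variable swelling after surgery would widen the postoperative spread, which also affects how well a weight of 1 fits.

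What is at stake is precision on a secondary endpoint. The plan says its endpoints must reach significance for TXA to be called effective, and it states no power for swelling, so there is no known margin to spare.

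**Working it through.** **Plan's own figure.** There is none to reproduce for swelling. The stated power calculation names no endpoint and does not enter here.

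**Inputs.** From the documents: the post/pre ratio, unadjusted tests, and 55 enrolled per cohort. Not in the documents, so assumed: rho, the within-cohort correlation of log preoperative and log postoperative circumference, and k = SD(log pre)/SD(log post).

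**Formula.** Write s² for the variance of log postoperative circumference.
- Log ratio (log post minus log pre): variance s²(1 + k² − 2·rho·k).
- ANCOVA residual: variance s²(1 − rho²).
- Relative variance, ANCOVA to log ratio: (1 − rho²)/(1 + k² − 2·rho·k).

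The denominator minus the numerator is k² − 2·rho·k + rho² = (k − rho)². This is never negative, and it is zero only when k = rho, that is, when the slope rho/k equals 1. With k = 1 the formula reduces to (1 + rho)/2.

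The plan would test the raw ratio, not its log. For changes of a few percent (an assumption), the log ratio is close to the ratio minus 1, so the comparison carries over.

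**Results.** The last column is 55 times the relative variance: the patients per cohort with which ANCOVA would match the precision of the ratio analysis at 55.

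| rho | k | slope rho/k | 1 − rho² | 1 + k² − 2·rho·k | relative variance | equivalent to 55 |
|---|---|---|---|---|---|---|
| 0.9 | 0.9 | 1.00 | 0.19 | 0.19 | 1.00 | 55 |
| 0.98 | 1 | 0.98 | 0.0396 | 0.04 | 0.99 | 54 |
| 0.95 | 1 | 0.95 | 0.0975 | 0.10 | 0.975 | 54 |
| 0.9 | 1 | 0.90 | 0.19 | 0.20 | 0.95 | 52 |
| 0.7 | 1 | 0.70 | 0.51 | 0.60 | 0.85 | 47 |
| 0.9 | 1.1 | 0.82 | 0.19 | 0.23 | 0.83 | 45 |
| 0.5 | 1 | 0.50 | 0.75 | 1.00 | 0.75 | 41 |

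**What the ratio already achieves.** Relative to analysing postoperative circumference alone, at rho 0.9 and k = 1 the log ratio leaves 0.20 of the variance and ANCOVA 0.19. They remove 80% and 81%.

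**Cost of estimating the slope.** The formula is a large-sample one. With 55 per cohort the error degrees of freedom fall from 108 to 107. For a normally distributed baseline the variance rises by a factor of about 1 + 1/(2×55 − 4) = 1.009. A 1% gain, as at rho 0.98 with k = 1, is cancelled by this; the larger gains are not.

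**Validity.** In simulations at 55 per cohort (assumed baseline mean 38 cm, SD 3 cm, 5% swelling; 8,000 runs per setting), the type I error of an independent-samples t-test on the ratio and of ANCOVA lay between 4.5% and 5.2%.

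**The case against.** The strongest reply is that this is a preference between two valid analyses. That stands: type I error is near 5% for both, and the divisor already does most of the work when repeat readings of the same knee are highly correlated. A reader might infer that the ratio is biased, or that chance imbalance in knee size passes straight into it. Neither is supported: removing knee size is what the divisor is for, and only a residual remains when the slope is not 1.

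A reader might also infer that any correlation below 1 makes the ratio over-correct. That is wrong. The condition is the slope: at rho = k = 0.9 the correlation is below 1 and the gain is zero.

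Nor should the table be turned into an expected rise in power. The documents give no rho, k, circumference SD or swelling effect, so any such figure would be the product of assumed inputs.

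Two further objections concern the plan itself. It does not settle on the post/pre ratio, because Methods and Procedures uses the contralateral limb. It also names a paired t-test, which does not fit two independent cohorts; of the tests named, only Mann-Whitney compares two groups. Both are separate and more serious faults. They narrow this point but do not remove it, since any unadjusted comparison of a post/pre ratio has the same limitation.

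Finally, the improvement needs no new data only if preoperative circumference is actually recorded, and it is neither listed nor scheduled. This is fair, but the plan's own ratio needs the same measurement.

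**Conclusion.** The point holds as a low-priority, near-costless improvement and not as an error. The planned ratio is valid. In large samples ANCOVA on the preoperative value is never less precise than the log-ratio comparison, and it is more precise whenever the log-scale slope differs from 1.

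Across the settings shown the reduction in variance runs from none to about 25%: at most 5% if rho is 0.9 or more with equal log-scale SDs, and 15% to 25% only with a moderate correlation (0.7 to 0.5) or a wider preoperative spread (k = 1.1). Those settings are illustrations and not bounds; the documents do not indicate where this trial lies. The consequence is limited because swelling is secondary and the sample size is not tied to it.

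**What to change.** In the Data Analysis and Statistical Plan, replace the swelling test with one sentence: log postoperative mean circumference at each postoperative time (immediately after surgery and at one week) will be analysed by ANCOVA with cohort as factor and log preoperative mean circumference of the same knee as covariate. Report the adjusted effect, back-transformed to a ratio, with a 95% CI. Keep the swelling ratio as a descriptive summary by cohort.

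Two edits go with it:
- Settle one reference measurement, so that Study Design, Methods and Procedures and the analysis section agree. If the contralateral limb is retained, enter its log circumference as the covariate instead of using it as a divisor.
- Add the preoperative circumference to the list of preoperative data in Methods and Procedures, at the same two patellar sites as the postoperative reading.

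The cost is a few lines of text and one degree of freedom. No measurement is needed beyond what the post/pre ratio already requires.

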#### **Primary Objective**

The primary objective of the study is to determine if there are any differences in blood loss between patients undergoing BTB anterior cruciate ligament reconstruction who receive TXA compared to patients who do not receive it.

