#### Secondary Objective

Secondary objective of the study is to determine is there is a difference in post operative pain and swelling between patients undergoing BTB anterior cruciate ligament reconstruction who receive TXA and patients who do not receive it.

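### The stated criterion for effectiveness, read literally, requires pain, blood loss and swelling all to be significant, which conflicts with blood loss as the sole primary objective

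*Combined protocol and SAP*

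**What the plan says.** The objectives are ranked. Under Primary Objective: "The primary objective of the study is to determine if there are any differences in blood loss". Under Secondary Objective: "Secondary objective of the study is to determine is there is a difference in post operative pain and swelling". Methods and Procedures gives the aim in the same direction: "The objective is to have the average blood loss of the cohort receiving TXA less than the cohort not receiving TXA".

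The Data Analysis and Statistical Plan drops the ranking: "We will use patient subjective pain, perioperative blood loss and knee swelling data as statistical endpoints". It next says "We are looking for a statistically significant difference in perioperative blood loss between the two cohorts", which again singles out blood loss. It then closes with the criterion: "The endpoints must be statistically significant between the two cohorts to show TXA is effective". That sentence does not say whether it means all the endpoints, any of them, or the primary one.

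No section gives a testing order or a multiplicity rule. The power statement (83% at the .05 level) names no endpoint and no sidedness.

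**The concern.** The closing sentence is a decision rule, and it is the only one in the document. *The endpoints* refers back to the three just listed, and *must* makes significance a requirement, so the literal meaning is that all three are needed. The hypothesis in the Rationale lends this some support, because it expects less bleeding to lead on to less swelling and pain.

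If the rule is applied as written, a significant blood-loss result is not enough, although it is exactly what the primary objective asks for. If the rule is not applied as written, the document does not say what replaces it, and the choice could be made after the results are seen.

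**Working it through.** **Inputs.** From the Data Analysis and Statistical Plan: significance level .05, power 83%, three endpoints. Assumptions, because the documents give none: two-sided between-cohort tests, approximately normal test statistics, and a common correlation ρ between endpoints of 0 to 0.7.

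**Step 1. The plan's own figure.** The plan states 83% power with 50 patients, an effect size of 0.5 and an SD of 2. Taking 50 per cohort and 0.5 as a standardised effect, power = Φ(0.5·√(50/2) − 1.96) = Φ(0.54) ≈ 0.71 two-sided, or Φ(2.5 − 1.645) ≈ 0.80 one-sided. The 83% is therefore not reproduced on these readings. That is a separate matter; 83% is used below only as the plan's stated value.

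**Step 2. A bound that needs no effect size or correlation.** With one deciding measure per endpoint, P(all three significant) ≤ P(the null endpoint is significant) = 0.05. So if TXA truly does nothing for pain, or nothing for swelling, the literal rule is met in at most 5% of trials, however strong the effect on blood loss.

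The one-measure condition matters. Methods and Procedures schedules VAS "at 0.5, 1, 1.5, 2, 4, 6, 24, and 48 hours as well as 7 days after surgery" (nine times), whereas Study Design says "Patients will be asked on postoperative day 1, 2 and 7 to rate their pain according to the VAS scale" (three days) and gives two postoperative swelling assessments. If significance at any listed time counted, a null pain endpoint would be significant in 37% of trials (nine independent times, 1 − 0.95⁹) down to 12% (correlation 0.9 between times). A null swelling endpoint would be significant in 10% down to 7% (two assessments). The 5% bound then no longer holds.

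**Step 3. Illustration of the power cost.** Suppose each endpoint had 83% power. At ρ = 0, all-three power = 0.83³ = 0.572. For ρ > 0 it comes from numerical integration over a shared normal component. The last column is 1 − (all-three power)/0.83.

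| ρ | All-three power | Rule not met, given significant blood loss |
|---|---|---|
| 0 | 0.572 | 31% |
| 0.3 | 0.622 | 25% |
| 0.5 | 0.659 | 21% |
| 0.7 | 0.702 | 15% |

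**Step 4. Type I error under each reading.**
- All three required, one measure each: at most 5%, so no inflation.
- Blood loss alone decides: 5%, so no adjustment is needed.
- Any one sufficient, one measure each: 1 − 0.95³ = 14.3% at ρ = 0, falling to 10.9% at ρ = 0.7; higher if each listed VAS and swelling time counts.

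**Step 5. Cost of making all three co-primary.** For 83% joint power, each test needs power 0.83^(1/3) = 0.940 at ρ = 0, or 0.912 at ρ = 0.7. The sample-size ratio to one test at 83% is [(1.960 + z)/(1.960 + 0.954)]², where z is the normal quantile of the per-test power. With z = 1.553 it is 1.45; with z = 1.353 it is 1.29.

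**The case against.** The strongest reply is that this is one loosely worded sentence against three consistent pointers: the primary objective, the aim in Methods and Procedures, and the analysis section's own statement that a significant blood-loss difference is sought. A later switch to pain or swelling would visibly contradict the stated objectives. This is fair, and it is why the repair is small. It does not remove the conflict, because the plural sentence is the only one that says what shows effectiveness, and the power statement cannot settle which reading was meant.

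A reader might infer more: that the missing multiplicity rule gives this trial an inflated type I error. The documents do not support that. Inflation arises only if any single endpoint were enough, and that is the reading the wording supports least.

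A reader might also take 57% to 70% as this trial's power. It is not an estimate. It rests on the stated 83% applying to every endpoint, and the plan gives no endpoint-specific effects. The differing VAS schedules likewise show that no deciding measure is named; they do not make this point more serious.

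**Conclusion.** The concern holds as a conflict between the literal effectiveness criterion and the ranked objectives. Its consequence is that a trial with a significant blood-loss result could be declared not to show effectiveness. The firm figure is the 5% ceiling when pain or swelling is truly unaffected, conditional on one deciding measure per endpoint. The shortfall to 57%–70% power is illustrative and depends on the unverified 83% and the assumed correlations. The all-three rule costs power without inflating type I error, and the absence of a multiplicity rule would on its own be only missing detail. The sentence should be corrected before unblinding, because it governs how the main result is interpreted.

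**What to change.** Replace the closing sentence of the Data Analysis and Statistical Plan with: *Effectiveness is judged on blood loss alone at the .05 level; pain and swelling are secondary and supportive.*

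Two further items are needed for that sentence to work, both settled before unblinding:
- **Sidedness.** State it as a design choice. The documents give none, and the aim in Methods and Procedures is directional; two-sided is the conventional choice.
- **One blood-loss measurement.** Study Design uses the drain volume when surgery ends. Methods and Procedures uses the intra-operative suction cup and also records estimated blood loss. The analysis section uses the suction drain after surgery. Reconcile the three and name the one that decides.

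This needs no extra patients or data. The downside is that the effectiveness claim is limited to blood loss.

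If all three endpoints are truly required, declare them co-primary in the objectives, name one deciding measure for each, and restate the power as joint power. Under the assumptions in Step 5, that takes about 29% to 45% more evaluable patients than a single endpoint at 83% power.

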## **Data and Safety Monitoring Plan**

Data monitoring will be done by [name], the anesthesiologist, and [name], the principal investigator will oversee the conduct of the study. They will review the following accumulated data quarterly.

They will monitor whether or not:

- 1. Collection and storage of patient data was performed in a sensitive and secure manner, as defined in the informed consent form and protocol, ensuring information is stored on REDCap.
- 2. All study activities were conducted with primary emphasis on patient care and wellbeing, ensuring the patients are not in discomfort and have an abnormally high VAS following the surgery.
- 3. If there were any adverse events, and if so were addressed appropriately and per protocol
- 4. The risk/benefit to patients has remained the same throughout the course of the study.

The study will be stopped if there are unexpected severe AE's in more than one patient. Adverse events will be defined as negative reactions to the intravenous TXA during or after surgery, including seizures, vision problems. We will submit summaries of data and safety monitoring annually.

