#### Version 2/26/20

indication for use nor support any other significant change in the labeling or advertising for the drug. The investigation does not involve a route of administration or dosage level or use in a patient population or other factor that significantly increases the risks (or decreases the acceptability of the risks) associated with the use of the drug product. The route of administration (IV) and dosage of 1 g has been shown to be safe and effective[13, 16]. The investigation is conducted in compliance with the requirements for institutional review set forth in part 56 and with the requirements for informed consent set forth in part 50; and The investigation is conducted in compliance with the requirements of 312.7.

We hypothesize that administration of TXA will reduce perioperative bleeding in BTB ACL reconstruction procedure with minimal side effects as compared to controls (no TXA). As a result, swelling and postoperative pain will decrease thus improving postoperative outcomes. By comparing two cohorts receiving the same procedure and administering TXA to one cohort, we can determine if the TXA affects perioperative bleeding and if decreasing perioperative bleeding will decrease postoperative pain and swelling.

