#### Version 2/26/20

medical histories will be performed based on their electronic medical records to identify any current pain medications or exclusion criteria. In order to maintain the blind, the resident assisting the surgeon will randomize the patient to one of two cohorts using REDCap. Both the resident and surgeon are members of the study team.

- Cohort 1: 1 gram of intravenous tranexamic acid (TXA) before tourniquet inflation and 1 gram of IV TXA before closure of the incision
- Cohort 2: Will not receive TXA.

The resident physician and anesthesiologist will not be blinded to the study, however the surgeon and study team members will remain blinded. Before the surgery begins, the resident will prepare the patient and the TXA will be administered (if assigned) before the tourniquet is placed, at which point the surgeon will be called into the room. The administration of TXA will not prolong the surgery and will not add any additional risks of prolonged anesthesia The surgeon will exit the surgery before closure at which point, the TXA will be administered (if assigned) and the resident physician will close the incision.

Immediate post-operative management will not be affected by this study. All patients will receive a standardized regimen of aspirin for DVT prophylaxis and Percocet for pain management, which is standard of care post-operative treatment.

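### Adverse events are defined as reactions to TXA, so the no-TXA cohort has none by definition and the cohorts cannot be compared on them

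*Combined protocol and SAP*

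**What the plan says.** - **Hypothesis (section I, Rationale).** TXA is expected to reduce perioperative bleeding "with minimal side effects as compared to controls (no TXA"). No rate, margin or threshold is attached to the side-effect part.
- **Cohorts (section III, Methods and Procedures).** "Cohort 2: Will not receive TXA". No placebo is described.
- **Definition (section III, Data and Safety Monitoring Plan).** "Adverse events will be defined as negative reactions to the intravenous TXA during or after surgery"; seizures and vision problems are given as examples. The same section stops the study if unexpected severe adverse events occur in more than one patient.
- **Symptom collection (section III, Methods and Procedures).** "Incidence of TXA-related side effects (nausea/vomiting, itching, anxiety, increased thirst, rapid heartbeat) in the first 24 hours will be noted". Follow-up lasts two weeks.
- **Analysis (section III, Data Analysis and Statistical Plan).** The plan provides "chi-squared and/or fisher's exact testing depending on size for binary variables". The endpoints it names are efficacy measures: "We will use patient subjective pain, perioperative blood loss and knee swelling data as statistical endpoints".
- **Serious events (section III, Adverse Event Reporting).** The principal investigator reports any SAE during prospective data collection to the IRB.

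**The concern.** A randomised safety comparison needs events counted by the same rule in both cohorts. Here the rule itself contains the exposure: an event is adverse only if it is a reaction to TXA. Patients who receive none cannot meet it, whatever happens to them. The control count is then a zero fixed by definition, not an observed rate.

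Several of the listed symptoms, such as nausea and vomiting, can occur in any patient after surgery and opioid analgesia. If such background symptoms were counted only where TXA was given, TXA would look harmful without being so. If attribution were withheld, little would be counted in either cohort. Control events that are never recorded may not be recoverable afterwards.

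The stopping rule is affected as well. Under the definition, only TXA-cohort patients can contribute to it, and only after someone has judged the event to be a reaction to TXA. The documents do not say who makes that judgement. The anesthesiologist, who is not blinded, is one of the two people monitoring the data.

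**Working it through.** **1. The provisions side by side.** The plan states no adverse event rate, safety margin or safety power, so there is no figure of its own to reproduce. The first step is a reading of the text.

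| Provision | Can a control patient contribute? | Scope |
|---|---|---|
| Adverse event definition | No, by definition | During or after surgery |
| Stopping rule | No, since it uses that term | Unexpected severe events |
| Five named symptoms | Unclear: not limited to one cohort, but labelled TXA-related | First 24 hours only |
| SAE reporting | Yes as worded (any SAE) | Serious events, reported to the IRB; no tabulation by cohort |

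Seizures and vision problems (named in the definition), chest pain and limb pain or swelling (listed under Risk), and the calf swelling and chest pain for which patients are told to seek care within seven days (Protection against Risks) are not among the five symptoms. Unless they are serious, no provision records them alike in both cohorts.

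**2. Illustration of the worst case.** Inputs from the documents: 55 per cohort (Number of Subjects), Fisher's exact test and the 0.05 level (Data Analysis and Statistical Plan). Assumptions: a two-sided test, the same true rate π in both cohorts, every TXA-cohort event attributed to TXA, and controls counted as 0/55.

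For k/55 against 0/55 with equal cohorts, the two-sided Fisher p-value is 2 × C(55,k) / C(110,k):

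- k = 5: p = 0.057
- k = 6: p = 0.027

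Six TXA-cohort events are therefore enough for significance. The chance of a spurious difference is P(X ≥ 6) with X ~ Binomial(55, π):

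| Assumed true rate, both cohorts | Controls fixed at 0/55 | Counted alike in both cohorts |
|---|---|---|
| 5% | 5.6% | not computed |
| 10% | 47.6% | 2.0% |
| 20% | 97.5% | 2.7% |
| 30% | over 99.9% | not computed |

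The last column comes from exact enumeration of Fisher's test over two independent binomial counts of size 55.

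**3. What symmetric counting could detect.** By the same enumeration, power is 56% for 20% against 40%, and 68% for 10% against 30%. A comparison of common symptoms is therefore feasible at this sample size, though only large differences would be found with reasonable probability.

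**The case against.** A reader might infer that the side-effect hypothesis cannot be tested at all. The documents do not support that. The hypothesis speaks of side effects, and Methods and Procedures has a separate collection for these. It sits in a list of data gathered on all patients (baseline data, pain scores, Percocet use, discharge times) and is not confined to Cohort 1. The TXA-related label followed by a bracketed list may simply name known side effects of the drug; no patient-by-patient causality step is described. The surgeon and study team are to remain blinded, and blinded staff could not record symptoms in one cohort only. A suitable test for binary variables exists. The SAE wording is not limited to TXA reactions, and since REDCap is used for randomisation, serious events could be tabulated by cohort.

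The large false-positive figures also need care. The fixed zero comes from the adverse event definition, whose examples are seizures and vision problems, and Risk lists seizures and trouble seeing as rare. Rates of 10% or more suit common symptoms, which belong to the other data stream. At 5% the figure is close to the nominal level. No safety endpoint is named, so the plan does not specifically assign this test to adverse events.

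All of that stands, and it limits the claim. It does not remove the conflict. The definition is exposure-dependent as written. The symptom list carries a label that can be read as attribution, and no section says it applies to controls whatever the cause. Even on the favourable reading it covers five symptoms for 24 hours of a two-week study. If an SAE is taken to be a serious form of the defined adverse event, the restriction carries over to SAEs too.

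**Conclusion.** The point holds in a limited form. Adverse events as defined cannot be compared between cohorts, which is at odds with a hypothesis stated against controls, and the stopping rule depends on attribution to TXA. This follows from the wording alone. Part of the side-effect hypothesis remains testable if the five symptoms are recorded identically in both cohorts, which the plan leaves unclear.

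The spurious-difference figures, from about 6% at a 5% rate to 97.5% at 20%, are not forecasts. They rest on assumed rates, full attribution in the TXA cohort, a zero control count and a two-sided Fisher test, and so describe the worst case under one reading. The change should be made, but it does not bear on the primary objective, which is blood loss.

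**What to change.** - **Data and Safety Monitoring Plan.** Define an adverse event as any untoward occurrence in either cohort during the study period, regardless of attribution. Record relatedness to TXA as a separate field.
- **Methods and Procedures.** Delete the TXA-related qualifier. State that the same symptom checklist is completed in the same way in both cohorts.
- **Data Analysis and Statistical Plan.** State that adverse event and symptom incidence will be tabulated and compared by randomised cohort with the chi-squared or Fisher test already provided.
- **Stopping rule.** Reconcile it with the revised definition, because a broader definition changes which events count towards it. No new clinical rule is proposed here.

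The cost is protocol wording and a CRF change, with slightly more recording. Reported event counts will be higher because background events are included.
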